5.7 Diet/Activity/Other Considerations

5.7.1 Diet

Subjects should maintain a normal diet unless modifications are required to manage an AE such as diarrhea, nausea or vomiting.

5.7.2 Contraception

Pembrolizumab may have adverse effects on a fetus in utero. Furthermore, it is not known if pembrolizumab has transient adverse effects on the composition of sperm.

For this trial, male subjects will be considered to be of non-reproductive potential if they have azoospermia (whether due to having had a vasectomy or due to an underlying medical condition).

Female subjects will be considered of non-reproductive potential if they are either:

(1) postmenopausal (defined as at least 12 months with no menses without an alternative medical cause; in women < 45 years of age a high follicle stimulating hormone (FSH) level in the postmenopausal range may be used to confirm a post-menopausal state in women not using hormonal contraception or hormonal replacement therapy. In the absence of 12 months of amenorrhea, a single FSH measurement is insufficient.);

Protocol Version: 04/10/2019

Page 29 of 72

OR

(2) have had a hysterectomy and/or bilateral oophorectomy, bilateral salpingectomy or bilateral tubal ligation/occlusion, at least 6 weeks prior to screening;

OR

(3) has a congenital or acquired condition that prevents childbearing.

Female and male subjects of reproductive potential must agree to avoid becoming pregnant or impregnating a partner, respectively, while receiving study drug and for 120 days after the last dose of study drug by complying with one of the following:

(1) practice abstinence[†] from heterosexual activity;

OR

(2) use (or have their partner use) acceptable contraception during heterosexual activity.

Acceptable methods of contraception are[‡]:

Single method (one of the following is acceptable):

- intrauterine device (IUD)
- vasectomy of a female subject's male partner
- contraceptive rod implanted into the skin

Combination method (requires use of two of the following):

- diaphragm with spermicide (cannot be used in conjunction with cervical cap/spermicide)
- cervical cap with spermicide (nulliparous women only)
- contraceptive sponge (nulliparous women only)
- male condom or female condom (cannot be used together)
- hormonal contraceptive: oral contraceptive pill (estrogen/progestin pill or progestinonly pill), contraceptive skin patch, vaginal contraceptive ring, or subcutaneous contraceptive injection

†Abstinence (relative to heterosexual activity) can be used as the sole method of contraception if it is consistently employed as the subject's preferred and usual lifestyle and if considered acceptable by local regulatory agencies and ERCs/IRBs. Periodic abstinence (e.g., calendar, ovulation, sympto-thermal, post-ovulation methods, etc.) and withdrawal are not acceptable methods of contraception.

‡If a contraceptive method listed above is restricted by local regulations/guidelines, then it does not qualify as an acceptable method of contraception for subjects participating at sites in this country/region.

Subjects should be informed that taking the study medication may involve unknown risks to the fetus (unborn baby) if pregnancy were to occur during the study. In order to participate in the study subjects of childbearing potential must adhere to the contraception requirement (described above) from the day of study medication initiation (or 14 days prior to the initiation of study medication for oral contraception) throughout the study period up to 120 days after the last dose of trial therapy. If there is any question that a subject of childbearing potential will not reliably comply with the requirements for contraception, that subject should not be entered into the study.

5.7.3 Use in Pregnancy

If a subject inadvertently becomes pregnant while on treatment with pembrolizumab, the subject will immediately be removed from the study. The site will contact the subject at least monthly and document the subject's status until the pregnancy has been completed or terminated. The outcome of the pregnancy will be reported to the Principal Investigator and to Merck without delay and within 24 hours to the Principal Investigator and within 2 working days to Merck if the outcome is a serious adverse experience (e.g., death, abortion, congenital anomaly, or other disabling or life-threatening complication to the mother or newborn).

The treating investigator will make every effort to obtain permission to follow the outcome of the pregnancy and report the condition of the fetus or newborn to the Lead Principal Investigator. If a male subject impregnates his female partner the study personnel at the site must be informed immediately and the pregnancy reported to the Lead Principal Investigator and to Merck and followed as described above and in Section 7.2.2.

5.7.4 Use in Nursing Women

It is unknown whether pembrolizumab is excreted in human milk. Since many drugs are excreted in human milk, and because of the potential for serious adverse reactions in the nursing infant, subjects who are breast-feeding are not eligible for enrollment.

5.8 Subject Withdrawal/Discontinuation Criteria

Subjects may withdraw consent at any time for any reason or be dropped from the trial at the discretion of the investigator should any untoward effect occur. In addition, a subject may be withdrawn by the investigator or the Principal Investigator if enrollment into the trial is inappropriate, the trial plan is violated, or for administrative and/or other safety reasons. Specific details regarding discontinuation or withdrawal are provided in Section 7.1.4 – Other Procedures.

Definition of Dose Limiting Toxicity: Any toxicity of >=Grade 3, any autoimmune toxicity >CTCAE Gr 2; DLT observation period is for the length of monotherapy for each cohort.

A subject must be discontinued from the trial for any of the following reasons:

- The subject or legal representative (such as a parent or legal guardian) withdraws consent.
- Confirmed radiographic disease progression

Note: A subject may be granted an exception to continue on treatment with confirmed radiographic progression if clinically stable or clinically improved.

- Unacceptable adverse experiences as described in Section 5.2.1.2
- Intercurrent illness that prevents further administration of treatment
- Investigator's decision to withdraw the subject
- The subject has a confirmed positive serum pregnancy test
- Noncompliance with trial treatment or procedure requirements
- The subject is lost to follow-up
- Completed 24 months of uninterrupted treatment with pembrolizumab or 35 administrations of study medication, whichever is later.

Note: 24 months of study medication is calculated from the date of first dose. Subjects who stop pembrolizumab after 24 months may be eligible for up to one year of additional study treatment if they progress after stopping study treatment provided they meet the requirements.

Administrative reasons

After the end of treatment, each subject will be followed for 30 days for adverse event monitoring (serious adverse events will be collected for 90 days after the end of treatment). Subjects who discontinue for reasons other than progressive disease will have post-treatment follow-up for disease status until disease progression, initiating a non-study cancer treatment, withdrawing consent or becoming lost to follow-up. After documented disease progression each subject will be followed by telephone for overall survival until death, withdrawal of consent, or the end of the study, whichever occurs first.

5.8.1 Discontinuation of Study Therapy after CR

Discontinuation of treatment may be considered for subjects who have attained a confirmed CR that have been treated for at least 24 weeks with pembrolizumab and had at least two treatments with pembrolizumab beyond the date when the initial CR was declared. Subjects who then experience radiographic disease progression may be eligible for up to one year of additional treatment with pembrolizumab via the Second Course Phase at the discretion of the investigator if no cancer treatment was administered since the last dose of pembrolizumab, the

subject meets the safety parameters listed in the Inclusion/Exclusion criteria, and the trial is open. Subjects will resume therapy at the same dose and schedule at the time of initial discontinuation.

5.9 Subject Replacement Strategy

5.10 Clinical Criteria for Early Trial Termination

Early trial termination will be the result of the criteria specified below:

- 1. Quality or quantity of data recording is inaccurate or incomplete
- 2. Poor adherence to protocol and regulatory requirements
- 3. Incidence or severity of adverse drug reaction in this or other studies indicates a potential health hazard to subjects
- 4. Plans to modify or discontinue the development of the study drug

In the event of Merck or Evelo decision to no longer supply study drug, ample notification will be provided so that appropriate adjustments to subject treatment can be made.

Protocol Version: 04/10/2019 Page 33 of 72

6.0 TRIAL FLOW CHART

6.1 Study Flow Chart

Trial Period:	Screening Phase		Treatment Cycles ^a							End of Treatment	Pos	t-Treatment	
							To be repeated beyond cycles						
Treatment Cycle/Title:	Study Screening	EDP1503 run-in ^b	1	2	3	4	5	6	7	8	Discon	Safety Follow-up	Follow Up Visits In
Scheduling Window (Days):	-21 to -1	± 3	± 3	± 3	± 3	± 3	± 3	± 3	± 3	± 3	At time of Discon	30 days post discon	Absence of Progression ^c Every 12 weeks post discon
Informed Consent	X												
Inclusion/Exclusion Criteria	X												
Demographics and Medical History	X												
Prior and Concomitant Medication Review	X	X	X	X	X	X	X	X	X	X	X	X	X
Pembrolizumab Administration			X	X	X	X	X	X	X	X			
Review Adverse Events	X	Xg	X	X	X	X	X	X	X	X	X	X	X
Physical Examination	X	X	X	X	X	X	X	X	X	X	X	X	X
Vital Signs and Weight	X	X	X	X	X	X	X	X	X	X	X	X	X
ECOG Performance Status	X	X	X	X	X	X	X	X	X	X	X	X	X
Pregnancy Test – Urine or Serum β-HCG	X												
CBC with Differential	X	X	X	X	X	X	X	X	X	X	X	X	
Comprehensive Serum Chemistry Panel	X	X	X	X	X	X	X	X	X	X	X	X	
Urinalysis	X												
TSH (with reflexive T3, FT4 as indicated)	X		X	X	X	X	X	X	X	X	X	X	

Protocol Version: 04/10/2019

Page 34 of 72

Trial Period:	Screening Phase			r.	Гreatm	ent Cyo	End of Treatment	Post-Treatment					
							To be repeated beyond 8 cycles						
Treatment Cycle/Title:	Study Screening	EDP1503 run-in ^b	1	2	3	4	5	6	7	8	Discon	Safety Follow-up	Follow Up Visits In
Scheduling Window (Days):	-21 to -1	± 3	± 3	± 3	± 3	± 3	± 3	± 3	± 3	± 3	At time of Discon	30 days post discon	Absence of Progression ^c Every 12 weeks post discon
Tumor Imaging (window includes all of cycle following drug administration)	X					X				X			
Archival or Newly Obtained Tissue Collection ^d	X^{d}		X ^d										
Correlative Studies Blood Collection ^e	X	X ^h	Xf			X					X		
Fecal Sample	X		X			X					X	X	

- a Treatment cycles = 21 days
- b EDP1503 alone run-in for two weeks (14 days) in cohort 1 and one week (7 days) in cohort two and continuous thereafter with pembrolizumab. An exception to this for cohort 2 patients will include any patient who is among the first three patients enrolled who will have a 2 week run in to monitor for EDP1503 toxicities especially. Cohort 2 cannot initiate the one week run-in until 3 patients have cleared two week EDP1503 run. Pembrolizumab will be administered on D1 of every cycle. EDP1503 will be taken po (2 capsules bid) for all 21 days of every cycle.
- c Patients who discontinue treatment without progression will have follow up visits for up to 2 years following drug discontinuation
- d Archival tissue for newly diagnosed metastatic melanoma is allowed in cohort 1. Fresh biopsies are otherwise required. Second biopsy at the end of the EDP1503 run-in period after at least 10 days in cohort 1 and at least 4 days in cohort 2.
- e Samples to be collected for correlative blood analysis are detailed in section 8.1.1.11
- f Sample to be taken prior to the initiation of pembrolizumab therapy
- g Nursing assessment for adverse events at 48 hours which can be completed by telephone.
- h Research cytokines, blood culture, whole blood

Protocol Version: 04/10/2019

Page 35 of 72

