Considering this background, we propose to collect peripheral blood for serum, peripheral blood mononuclear cells, germline DNA, as well as fecal samples throughout treatment. **Baseline tumor tissue prior to treatment and/or fresh tumor biopsy at baseline and at after EDP1503 run-in are required on all patients**. Diagnostic tissue from prior biopsy is allowed if the tissue was obtained by core or surgical biopsy (FNA is not acceptable) and no intervening systemic treatment has been administered. Peripheral blood for serum and blood mononuclear cells will be taken at the beginning and end of the run in period when subjects are only taking EDP1503 to evaluate any immediate effects on these biomarkers. Tumor

biopsy will be required at the end of the second week of EDP1503 run-in (prior to starting pembrolizumab) in patient's naïve to anti-PD1 (cohort 1) unless considered not clinically feasible. These biopsies will be analyzed to evaluate the effect of the EDP1503 on the tumor microenvironment.

Fecal samples will be analyzed by a variety of methods to determine quantitatively if there is a correlation between specific features of the host microbiome and/ or its manipulation with the effect on the systemic and tumor biomarkers. Analysis may include microbial culturing and nucleic acid based evaluation. Micro-organisms cultured from patient fecal samples may be stored and studied in preclinical models with the intent of learning more about the interaction between the microbiome and host immune responses.

Additionally, it is requested that any patients who undergo tumor biopsy as part of their standard care during the study have any available tissue forwarded for analysis in comparison of pre-administration and on-/post-treatment tumor microenvironmental factors.

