8.1.1.11 Tumor Tissue Collection and Correlative Studies Blood Sampling

The following tables outline the requirements for tissue and blood banking. These will be collected and stored for batched future analysis.

Biospecimen type	Collection Time Point	Number of
		samples per
		patient

Protocol Version: 04/10/2019

Page 39 of 72

Fecal sample	Pre administration of EDP1503	10 samples (2 samples each from
	Following run in of EDP1503	5 time points)
	At dose 4 of treatment with pembrolizumab	
	At discontinuation visit	
	30 days after cessation of EDP1503	
A paraffin-embedded tissue block of metastatic tumor taken before initiation of treatment.	Pre-treatment: obtained prior treatment on protocol	1 historical sample
Paraffin-embedded tissue block of metastatic tumor taken before initiation of treatment (if available).	Pre-treatment: obtained prior treatment on protocol	1 sample
Paraffin-embedded tissue block of metastatic tumor taken after EDP1503 run in. Where feasible this should be taken from the same metastatic or primary site as the initial biopsy.	Pre-treatment: obtained after the EDP1503 run in	1 sample
Peripheral Blood Mononuclear Cells: ~60 ml of anti-coagulated whole blood in green top tube	Pre-administration of EDP1503: 8-10 tubes taken within 21 days prior to EDP1503 administration. 8-10 tubes taken at the	Up to 40 samples total over 4 time points
	following time points:	
	(1) at day of dose 1 pre- administration of pembrolizumab	
	(2) dose 4 pembrolizumab	
	(3) at time of progressive disease.	
Whole blood for germline DNA: 8-10 mL of whole blood in PAXgene tube	Within 21 days prior to administration of EDP1503	1 sample
Cytokines	Pre administration of EDP1503	4 samples

Protocol Version: 04/10/2019 Page 40 of 72

	Following approximately 48 hours of EDP1503	
	Following run in of EDP1503	
	At dose 4 of treatment with pembrolizumab	
Blood Culture	Pre administration of EDP1503	2 samples
	Following run in of EDP1503	
EDP1503 PCR	Pre administration of EDP1503	2 samples
	Following run in of EDP1503	

Biospecimens will be shipped and stored in the University of Chicago Human Immune Monitoring Core Facility as below with the exception of one stool sample from each time point which will be sent to Evelo Biosciences.

Human Immune Monitoring Core:

Contact: [name] University of Chicago - Human Immune Monitoring Core [name]

[contact] [contact]

Ship human microbiome sample kits to*:

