The variance of baseline data due to sampling variation is provided by published studies on the variability of the TIS due to sampling (Walldren *et al.*) From the dataset of multiple samplings of a baseline sample, a ratio of paired baseline TIS scores (n=85) was calculated, median (IQR): 0.9 (.25). To determine whether a difference in TIS score from day 14 to baseline is statistically significant from replicate TIS measurements, a 95% Bca confidence interval was constructed from 10000 bootstrap replicates using the ratios of paired baseline TIS scores, (0.81,1.31). Based on this estimate, a TIS ratio score > 1.31 would suggest a significant result at the 95% confidence level.

Association of the TIS with response rate (either deep response of > 80% in Cohort 1 or RECIST response rate in Cohort 2) and PFS will be analyzed following the established methods of (Ayers *et al.*).

Several outcomes may be envisaged:

- EDP1503 causes increase in TIS in a subset of patients and that increase is associated with an increase in RR and PFS.
- Baseline TIS is associated with PFS, and changes induced by EDP1503 treatment are not associated with changes in RR and PFS.
- EDP1503 does not affect TIS in any patient.

These hypotheses will be explored using linear mixed effects models fitted to immunological parameters and related composite scores to determine associations of rate of change with treatment outcome, following the strategy of Ribas *et al*.

We will also perform additional exploratory analyses.

In addition to the TIS, the IO360 panel provides for the individual semi-quantitative enumeration of multiple cell types including NK, DC, and T cells, which will be enumerated in pre and post treatment biopsies.

The immunofluorescense assays will additionally provide quantitation of immune cell types. The ability to sample multiple portions of each pre and post treatment sample with IF will allow for high-dimensional resolution of group differences determined by Wilcoxon rank-sum test. These results will be cross correlated with the Nanostring analysis, and the quality of the correlation compared to Ribas *et al*.

References:

Danaher P et al. Gene expression markers of Tumor Infiltrating Lymphocytes. JITC 5:18-33 (2017)

Ayers *et al.* IFNg related mRNA profile predicts clinical response to PD-1 blockade. JCI 127(8):2930-2940 (2017)

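### Cohort 1 TIS pairs may set archival tissue against a new biopsy from another lesion, and the plan does not show that its 1.31 limit covers those differences

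*Combined protocol and SAP*

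**What the plan says.** Baseline tissue: footnote d of section 6.1 states "Archival tissue for newly diagnosed metastatic melanoma is allowed in cohort 1" and otherwise asks for fresh biopsies. Section 4.2.3.2 adds conditions: "Diagnostic tissue from prior biopsy is allowed if the tissue was obtained by core or surgical biopsy", fine-needle aspirates are excluded, and tissue counts only if "no intervening systemic treatment has been administered". Neither section sets a maximum age for the tissue.

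Post-run-in tissue: footnote d asks for a "Second biopsy at the end of the EDP1503 run-in period after at least 10 days in cohort 1". On its location, the table in section 8.1.1.11 says "Where feasible this should be taken from the same metastatic or primary site as the initial biopsy". The same table lists one historical block and a further pre-treatment block to be supplied if there is one.

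Analysis: the biopsy part of section 10.1 makes a therapy-induced change in TIS its primary hypothesis. Its yardstick is described this way: "From the dataset of multiple samplings of a baseline sample, a ratio of paired baseline TIS scores (n=85) was calculated", with median 0.9 and IQR 0.25. A bootstrap interval of 0.81 to 1.31 follows, and a ratio above 1.31 is taken as significant at the 95% level. The section does not separate pairs by tissue age or lesion, does not adjust for either, and plans no sensitivity analysis on them. Section 5.3 confirms that nothing is randomized.

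**The concern.** A Cohort 1 ratio can contain three things besides drug effect: repeat-sampling noise, a difference between lesions, and whatever changed between the archival sample and the new biopsy. The limit is described only in terms of the first. If the other two add variation, more unchanged patients cross 1.31. If archival and new tissue differ systematically, the average ratio moves as well.

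The biopsy pair carries weight because it is the only planned look at the tumour under EDP1503 alone. The flow chart schedules imaging at screening and at cycles 4 and 8, and no untreated pairs are collected. One outcome that section 10.1 envisages is a TIS rise in a subset of patients, linked to response and PFS. Calls above 1.31 are a natural way to form that subset, and false members would blur the link.

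**Working it through.** **Inputs.** From section 10.1: median ratio 0.9, IQR 0.25, n = 85, interval (0.81, 1.31). From section 10.2: 35 evaluable patients in Cohort 1. Assumed, because the documents give no figure: how much lesion and time differences add to the spread.

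**The plan's own figure.** The interval (0.81, 1.31) cannot be reproduced. The 85 ratios are not given and the bootstrapped statistic is not named. Approximations from the median and IQR give:
- BCa interval for the median: about 0.84 to 0.95.
- 95% range for single ratios: about 0.54 to 1.26 (normal) or 0.60 to 1.35 (lognormal).

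Only the upper end of a single-ratio range lies near 1.31. Treating 1.31 as a limit for one patient's ratio is therefore an interpretation, though it matches how the SAP uses it.

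**Spread of the log ratio.** With quartiles placed symmetrically at 0.775 and 1.025:

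s = ln(1.025/0.775)/1.349 = 0.207

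**Chance that an unchanged pair exceeds 1.31.** With null centre 0.9 and SD multiplier k:

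P = 1 − Φ( ln(1.31/0.9) / (k·s) ), where ln(1.31/0.9) = 0.375

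| k (assumed above 1) | k·s | P(ratio > 1.31) | Expected of 35 if all pairs affected |
|---|---|---|---|
| 1 | 0.207 | 3.5% | 1.2 |
| 1.5 | 0.311 | 11.4% | 4.0 |
| 2 | 0.415 | 18.3% | 6.4 |

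**Only some pairs affected.** With a share f affected, the count is 35 × [(1 − f) × 0.035 + f × P].
- f = 25%: 1.9 (k = 1.5) or 2.5 (k = 2).
- f = 50%: 2.6 or 3.8.

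**Sensitivity to the set-up.**
- Null centre 1.0 instead of 0.9: 9.6%, 19.3% and 25.7% for k = 1, 1.5 and 2.
- Added rather than multiplied variation, centre 0.9, log SD 0.205 (IQR matched exactly to a lognormal): 3.4% with nothing added, 9.5% with an added log SD of 0.2, 20.2% with 0.4.
- 1.31 taken as the 97.5th percentile about 1, so s = ln(1.31)/1.96 = 0.138: 2.5%, 13.3% and 26.2% for the same additions.

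The level depends on these choices. In every version the rate rises with added variation.

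**Systematic shift, for illustration.** Suppose all 35 pairs drifted upward by 10% with no drug effect and log SD stayed at 0.205. A two-sided 5% test of the mean log ratio has z = ln(1.1)/(0.205/√35) = 2.75, so it would reject with probability about Φ(2.75 − 1.96) = 78%. With an added log SD of 0.2 this is 50%. The 10% is an assumption.

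**The case against.** The protocol contains real safeguards. Archival tissue must come from newly diagnosed metastatic disease, by core or surgical biopsy, with no systemic treatment in between. The same site is the default where feasible. A further pre-treatment block may exist, and under footnote d archival baseline tissue is confined to Cohort 1. These conditions narrow the problem. They do not remove lesion or time differences, and section 10.1 does not say which block is the baseline of the ratio.

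A reader might also infer more than the documents support:
- *That baseline tissue may be of any age.* The conditions above limit it. What is missing is a stated maximum.
- *That archival and new samples are prepared differently.* Section 8.1.1.11 lists all the tumour samples as paraffin-embedded blocks, so no preparation difference is documented.
- *That the 1.31 limit contains no lesion or time variation.* The 85 ratios come from a cited abstract that cannot be checked here. The SAP simply does not show that these sources are included.
- *That every lesion difference passes for a drug effect.* Random differences inflate per-patient crossings but do not bias a cohort mean. Only a systematic shift does, and the documents give neither its size nor its direction.
- *That 4 to 6 false calls are to be expected.* That count assumes every one of 35 patients has an affected pair. Archival baseline is optional, and section 4.2.3.2 lets the second biopsy in Cohort 1 be omitted when it is not clinically feasible.

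Finally, tumour immune change is an exploratory objective (section 3.3). No sample size or efficacy rule in section 10.1 depends on TIS.

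**Conclusion.** The concern holds as a limited one. As written, the plan judges unlike pairs by one limit whose described source is repeat sampling, and reads the result as an effect of therapy without a control.

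Without added variation, about 3.5% of unchanged pairs exceed 1.31. At assumed SD factors of 1.5 and 2 this is 11% and 18%, with 4 to 6 of 35 as an upper bound. These figures rest on a lognormal shape, a null centre of 0.9 and 1.31 acting as a single-patient limit. The direction of the effect does not rest on the factors chosen. Bias in the mean change is possible but cannot be sized from the documents. The primary efficacy conclusions are untouched.

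**What to change.** Record the date and the lesion of each tumour sample on the CRF. In section 10.1, specify before results are seen that:
- the TIS change and the calls above 1.31 are reported separately for newly obtained same-lesion pairs and for archival or different-lesion pairs;
- a change is attributed to EDP1503 only if it appears in the newly obtained same-lesion pairs;
- 1.31 is not used as a 95% limit for the other pairs.

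The cost is SAP wording and two CRF fields, with no new biopsies. The drawback is that fewer pairs support the attribution. Those pairs may also be a selected group, since a surgically removed lesion cannot be sampled again. Reporting the other pairs alongside keeps their information and shows how far any apparent effect depends on unlike tissue.
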